### 7.2.2. Exclusion Criteria Based on Treatment History

6. Subject has a history of treatment resistance, defined as failure to respond to 2 adequate trials of different antipsychotic medications (a minimum of 4 weeks at the subject’s maximum tolerated dose)
7. Subject has used clozapine within 6 months prior to screening or has a history of clozapine use for treatment-resistant schizophrenia
8. Subject has a history of poor or inadequate response to treatment with olanzapine
9. Subject received olanzapine, mesoridazine, chlorpromazine, or thioridazine at any time during the past 6 months or long-acting injectable antipsychotic medication in the last 6 months with the exception of 3-month paliperidone which must not have been received within the past 12 months
10. Subject requires or has had electroconvulsive therapy (ECT) treatment in the 2-month period prior to screening

**7.2.3. Exclusion Criteria Based on Drug/Alcohol Use and Concomitant Meds**

11. Subject has a diagnosis (based on DSM-5 criteria) of moderate or severe alcohol or drug use disorder currently or at any time during the 3 months prior to screening.
12. Subject has a positive urine drug screen for opioids, amphetamine/ methamphetamine, phencyclidine, or cocaine at screening
13. Subject has taken opioid agonists (eg, codeine, oxycodone, tramadol, or morphine) within the 14 days prior to screening and/or anticipates a need to take opioid medication during the study period (eg, planned surgery) or has taken opioid antagonists within 60 days prior to screening
14. Subject is taking any weight loss agents or hypoglycemic agents at screening
15. Subject is currently on a statin medication (an HMG-CoA reductase inhibitor) that was initiated or has had a dose adjustment within the 3 months prior to screening

**7.2.4. Exclusion Criteria Based on Medical Conditions/Medical History**

16. Subject has known risk of narrow-angle glaucoma
17. Subject has a clinically significant or unstable medical illness, condition, or disorder that would be anticipated to potentially compromise subject safety or adversely affect the evaluation of efficacy, including (but not necessarily limited to) the following:
  - Clinically significant hypotension or hypertension not stabilized by medical therapy
  - Unstable thyroid dysfunction in the past 6 months (eg, hypothyroidism, hyperthyroidism, or thyroiditis that was untreated, or discovered and treatment was initiated within the 6 months prior to screening)
  - Personal or family history of neuroleptic malignant syndrome, has a history of clinically significant extrapyramidal symptoms when taking olanzapine, or has had clinically significant tardive dyskinesia or tardive dystonia within 30 days of screening
  - Inflammatory bowel disease or any other gastrointestinal (GI) disorder associated with weight loss, anorexia nervosa, bulimia nervosa, or binge eating disorder
  - Neurologic conditions including the following:
    - History of seizure disorder or a condition associated with seizures (exception: history of febrile seizures)
    - History of brain tumor, subdural hematoma or other clinically significant neurological condition within the 12 months prior to screening
    - Head trauma with loss of consciousness within the 12 months prior to screening
    - Active acute or chronic central nervous system (CNS) infection
    - Stroke within the 6 months prior to screening

- A cardiac condition that might confound the results of the study or pose additional risk when administering the investigational agents to the subject or preclude successful completion of the study including the following:
  - Clinically significant cardiac arrhythmia, cardiomyopathy, or cardiac conduction defect, a history of myocardial infarction or unstable angina within 3 months prior to screening

18. Subject has a history of diabetes

19. Subject has undergone a significant blood loss (>500 mL) or blood product donation (including platelets or plasma) within 60 days of screening or anticipates blood or blood product donation at any time during the trial

#### **7.2.5. Exclusion Criteria Based on Laboratory Assessments at Screening**

20. Subject has any of the following lab results at screening:

- Hemoglobin A1c (HbA1c)  $\geq 6.0\%$
- Dyslipidemia, defined for this study as total fasting cholesterol >280 mg/dL or fasting triglycerides >500 mg/dL
- Aspartate aminotransferase (AST) or alanine aminotransferase (ALT) value  $\geq 2$  times the upper limit of the laboratory normal reference range
- Absolute neutrophil count  $\leq 1.5 \times 10^3 \mu\text{L}$
- Platelet count  $\leq 75 \times 10^3 \mu\text{L}$
- Serum creatinine >2.5 mg/dL
- Positive pregnancy test result

21. Positive serology test for hepatitis B surface antigen, hepatitis C antibody (confirmed by RNA testing), or human immunodeficiency virus (HIV) antibody at screening

22. Clinically significant ECG abnormality at Visit 1 or baseline Visit 2

23. QT interval >450 msec for men and >470 msec for women, as corrected by the Fridericia formula (QTcF), observed at Visit 1 or baseline Visit 2

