3. DATA ANALYSIS

3.1. General Statistical Methodology

Baseline for efficacy or safety analysis is defined as the last non-missing efficacy or safety assessment on or before the first dose of study drug in the Double-blind Treatment Period.

In general, descriptive statistics: n, mean (SD), median, minimum, and maximum, for continuous variables and number and percentage of subjects in each category for categorical variables will be provided by treatment group for all variables.

All statistical tests and confidence intervals (CIs), unless stated otherwise, will be 2-sided and will be set at an alpha level of 0.05.

Unless specified otherwise, all formal comparisons will be between ALKS 3831 and placebo groups. An exploratory analysis will be conducted between olanzapine and placebo groups.

All source data will be presented as subject data listings.

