3.9.2. Clinical Laboratory Parameters

Laboratory parameters will be presented in conventional (ie, US) units. Only scheduled laboratory parameters will be included in the summaries. All laboratory data, including those collected at unscheduled visits, will be included in the listings.

Laboratory results (baseline and change from baseline) for the Safety population for chemistry and hematology parameters will be summarized by treatment group and by visit.

Number (percentage) of subjects with potentially clinically significant (PCS) values at any post-baseline visit, will be summarized by treatment group. PCS criteria are presented in [Table 1](#). The denominator is all subjects with non-PCS baseline and at least one post-baseline assessment in the Safety Population and the numerator is the number of subjects with non-PCS baseline and PCS at post-baseline. All PCS values including baseline PCS values will be included in supportive listings.

Shift tables for selected metabolic parameters (glucose, total cholesterol, LDL, HDL, tryglyceride, and HbA1c) and liver function tests will be presented. The criteria are summarized in [Table 2](#), [Table 3](#) and [Table 4](#).

Table 1: Criteria of Potentially Clinically Significant (PCS) Abnormality for Selected Analytes

Parameters	Criteria
Chemistry	
Albumin	<2.5 g/dL
Alkaline Phosphatase (U/L)	$\geq 3 \times \text{ULN}$
Alanine Aminotransferase (U/L)	$\geq 3 \times \text{ULN}$
Aspartate Aminotransferase (U/L)	$\geq 3 \times \text{ULN}$
Bilirubin, Total	$\geq 2.0 \text{ mg/dL}$
Blood Urea Nitrogen	>30 mg/dL
Cholesterol, Random	>300 mg/dL
Cholesterol, Fasting	$\geq 240 \text{ mg/dL}$
Cholesterol, HDL Fasting	$\leq 30 \text{ mg/dL}$
Cholesterol, LDL Fasting	$\geq 160 \text{ mg/dL}$
Creatine Kinase (U/L)	$\geq 3 \times \text{ULN}$
Creatinine	$\geq 2.0 \text{ mg/dL}$
Glucose, Random	<50 mg/dL or $\geq 200 \text{ mg/dL}$
Glucose, Fasting	<50 mg/dL or $\geq 126 \text{ mg/dL}$
Potassium	<3 mmol/L or >5.5 mmol/L
Lactate Dehydrogenase (U/L)	$> 3 \times \text{ULN}$
Prolactin (Female)	>30 ng/mL
Prolactin (Male)	>20 ng/mL
Sodium	<130 mmol/L or >150 mmol/L
Triglycerides, Fasting (Female)	$\geq 120 \text{ mg/dL}$
Triglycerides, Fasting (Male)	$\geq 160 \text{ mg/dL}$

Table 1: Criteria of Potentially Clinically Significant (PCS) Abnormality for Selected Analytes (Continued)

Parameters	Criteria
Hematology	
Eosinophils	$>1.0 \times 10^3/\mu\text{L}$
Hematocrit (Female)	$\leq 32\%$
Hematocrit (Male)	$\leq 37\%$

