Neutrophils, Absolute	$<1.5 \times 10^3/\mu\text{L}$
Platelets	$<75.0 \times 10^3 \text{ cells}/\mu\text{L}$ or $\geq 700.0 \times 10^3 \text{ cells}/\mu\text{L}$
Leukocytes	$\leq 2.8 \times 10^3/\mu\text{L}$ or $\geq 16.0 \times 10^3/\mu\text{L}$

Table 2: Shifts Category from Baseline to Any Post-Baseline for Selected Lipid Parameters

Total cholesterol (fasting) mg/dL
Normal (<200) to high (≥ 240)
Borderline (≥ 200 and < 240) to high (≥ 240)
Normal/Borderline (<240) to high (≥ 240)
Normal (<200) to borderline/high (≥ 200)
Increase ≥ 40 mg/dL
LDL Cholesterol (fasting) mg/dL
Normal (<100) to high (≥ 160)
Borderline (≥ 100 and <160) to high (≥ 160)
Normal/borderline (<160) to high (≥ 160)
Normal (<100) to borderline/high (≥ 100)
Increase ≥ 30 mg/dL
HDL Cholesterol (fasting) mg/dL
Normal (≥ 40) to low (<40)
Decrease ≥ 20 mg/dL
Triglycerides (fasting) mg/dL
Normal (<150) to high (≥ 200)
Normal (<150) to very high (≥ 500)
Borderline (≥ 150 and <200) to high (≥ 200)

Borderline (≥ 150 and < 200) to very high (≥ 500)
Normal/borderline (< 200) to high (≥ 200)
Normal/borderline (< 200) to very high (≥ 500)
Normal (< 150) to borderline/high/very high (≥ 150)
Increase ≥ 50 mg/dL

Table 3: Shift Category from Baseline to Any Post-Baseline in Glucose and HbA1c

Serum glucose (fasting) mg/dL
Normal (< 100) to high (≥ 126)
Impaired (≥ 100 and < 126) to high (≥ 126)
Normal/Impaired (< 126) to high (≥ 126)
Increase ≥ 10 mg/dL
HbA1c %
Shift from baseline ($< 5.7\%$) to post-baseline $\geq 5.7\%$
Shift from baseline ($< 5.7\%$) to post-baseline $\geq 5.7\%$ and $< 6.5\%$
Shift from baseline ($< 5.7\%$) to post-baseline $\geq 6.5\%$

Table 4: Shift Category from Baseline to Any Post-Baseline in Liver Function Test

Alanine Aminotransferase (ALT) (U/L)
Shift from Normal to ≥ 3 x ULN
Shift from Normal to ≥ 5 x ULN
Shift from Normal to ≥ 10 x ULN
Aspartate Aminotransferase (AST) (U/L)
Shift from Normal to ≥ 3 x ULN
Shift from Normal to ≥ 5 x ULN
Shift from Normal to ≥ 10 x ULN
Bilirubin, Total (mg/dL)
Shift from Normal to > 1 xULN
Shift from Normal to ≥ 2 xULN

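### SAP Table 4 grades ALT and AST at 5x and 10x ULN only for subjects who start normal, although the protocol admits subjects up to just under 2x ULN

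*Protocol*

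**What the plan says.** **Entry.** Protocol 7.2.5, exclusion 20, applies when the "Subject has any of the following lab results at screening"; the liver item is an "Aspartate aminotransferase (AST) or alanine aminotransferase (ALT) value" of at least 2x ULN. The list contains no bilirubin limit.

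**Baseline.** SAP 3.1: "Baseline for efficacy or safety analysis is defined as the last non-missing efficacy or safety assessment on or before the first dose of study drug". The protocol's schedule includes predose laboratory samples on Day 1, so the analysis baseline will usually be the Day 1 value, not the screening value on which eligibility was judged.

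**Graded liver table.** SAP Table 4 has eight rows: ALT at 3x, 5x and 10x ULN, AST at the same three levels, and total bilirubin above 1x and at 2x ULN. Each row begins "Shift from Normal to". Table 4 gives no numeric limit for normal and no denominator.

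**PCS table.** SAP Table 1, "Criteria of Potentially Clinically Significant (PCS) Abnormality for Selected Analytes", has one level each for ALT and AST, 3x ULN or more, and one for total bilirubin, 2.0 mg/dL or more. SAP 3.9.2 sets the counting rule: "The denominator is all subjects with non-PCS baseline and at least one post-baseline assessment in the Safety Population". Those among them who later reach the PCS level make up the count. On listings it adds: "All PCS values including baseline PCS values will be included in supportive listings".

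**The concern.** The entry rule and the graded table do not cover the same people. Subjects with mildly raised transaminases are eligible by design, yet the only by-arm rows that separate a 3x from a 5x or 10x elevation are restricted to subjects who began in the normal range. The subjects left out are those who start nearest to the thresholds.

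Safety and tolerability is the trial's secondary objective. Marked transaminase elevations are likely to be few in a four-week study, so one event missing from the 5x or 10x row of one arm could change how that row reads.

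Elsewhere the SAP allows for raised baselines. For total cholesterol, LDL, triglycerides and fasting glucose, Tables 2 and 3 add rows that start from borderline or impaired values, combined rows that start anywhere below the high threshold, and rows for absolute increase. Table 4 has no counterpart to these.

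**Working it through.** The plan states no figure to reproduce here. The check applies the table rules to example subjects, then asks how much could be involved.

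**Rules applied.**
- Table 4 row at k x ULN (k = 3, 5, 10): baseline normal and peak at least k x ULN. Normal is taken as no more than 1x ULN, an assumption because Table 4 does not define it.
- Table 1 PCS row: baseline below 3x ULN and peak at least 3x ULN.

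**Result, in multiples of ULN for one analyte.**

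| Baseline | Peak | Table 4 rows entered | Table 1 PCS row |
|---|---|---|---|
| 0.8 or 1.0 | 5 | 3x, 5x | yes |
| 0.8 or 1.0 | 10 | 3x, 5x, 10x | yes |
| 1.2 or 1.9 | 3 | none | yes |
| 1.2 or 1.9 | 5 | none | yes |
| 1.2 or 1.9 | 10 | none | yes |
| 3.2 | 10 | none | no |

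The rows for 1.2 and 1.9 are the point: such a subject is detected at 3x ULN by Table 1 but not graded above it in any by-arm count. The last row lies above the entry limit and could arise only if the value rose between screening and Day 1. The rule works analyte by analyte: a subject raised on ALT alone drops out of the ALT rows, not the AST rows.

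**How many subjects.** The share p with a raised baseline is not in the documents. Assuming 5% to 20%:
- 130 x 0.05 = 6.5, and 130 x 0.20 = 26, so about 7 to 26 per arm.
- 390 x 0.05 = 19.5, and 390 x 0.20 = 78, so about 20 to 78 in all.

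**Effect on counts.** Let r be the risk of reaching 5x ULN among normal starters and k the relative risk for raised starters, also not in the documents. The share of such events missing from the 5x row is pk / (pk + 1 - p):
- p = 0.05, k = 1: 0.05 / (0.05 + 0.95) = 0.05
- p = 0.10, k = 3: 0.30 / (0.30 + 0.90) = 0.25
- p = 0.20, k = 5: 1.00 / (1.00 + 0.80) = 0.56

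**Effect on percentages.** If Table 4 percentages use normal starters as the denominator, the table shows r, while the risk in all subjects is r(1 - p + pk):
- k = 1: equal to r, so no distortion.
- p = 0.10, k = 3: 1.2r, so the table is low.
- p = 0.10, k = 0.5: 0.95r, so the table is slightly high.

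**In subjects.** With p = 0.10, k = 3 and an assumed r of 0.5% to 2%, the expected number missing from the 5x row is 130 x 0.10 x 3 x 0.005 = 0.2 to 130 x 0.10 x 3 x 0.02 = 0.8 per arm.

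**The case against.** The strongest reply is that nothing is hidden. Table 1 counts these subjects by arm at 3x ULN or more from any non-PCS baseline, the listings show every PCS value, and the chemistry summaries by visit and arm include a maximum. Under Protocol 13.1, a value the investigator judges clinically significant is also recorded as an adverse event. For bilirubin, Table 1 counts 2.0 mg/dL or more from any lower baseline, including a raised one. All of this stands, and it makes the gap one of grading, not of detection. It does not close the gap. A listing is not a count by arm. A maximum gives one value per visit and arm, not a number of subjects. Adverse event severity under Protocol 13.4 is judged by interference with usual activities, not by multiples of ULN.

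A reader might infer three stronger things, none of which the documents support.

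- *That raised-baseline subjects vanish from the liver summaries.* They do not; they are in the Table 1 row.
- *That Tables 1 and 4 contradict each other at 3x ULN.* They are two summaries with different baseline conditions, and shifts from a normal range are an ordinary device; the HbA1c rows of Table 3 all start from below 5.7%. The counts need not agree, but that is not an error.
- *That liver severity is understated.* The counts at 5x and 10x can be incomplete, but bias in a percentage depends on Table 4's unstated denominator and on a relative risk that no document gives.

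It is also fair to say that nothing is wrong with exclusion 20 itself. The point concerns the SAP table only.

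**Conclusion.** The point holds as a gap in grading. A subject who enters above normal on ALT or AST and reaches 5x or 10x ULN on that analyte is counted by arm only as 3x or more, so the planned 5x and 10x tiers can omit marked elevations. This follows from the table rules alone, given only that normal means no more than 1x ULN.

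Its size is uncertain. About 7 to 26 subjects per arm would fall outside the graded rows if 5% to 20% enter above ULN, and the expected number of missed events is probably below one per arm under the illustrative risks used. Both ranges rest on assumptions. The primary and key secondary analyses are untouched. It is worth correcting because the correction costs almost nothing and makes a safety count complete.

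**What to change.** In SAP Table 4, or as added levels in Table 1:

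1. Count ALT and AST at 3x, 5x and 10x ULN among subjects whose baseline is below that row's own threshold (below 3x, below 5x, below 10x).
2. Count bilirubin at 2x ULN from a baseline below 2x ULN.
3. State matching denominators: subjects with a baseline below the row's threshold and at least one post-baseline value.
4. Keep the existing from-normal rows as supportive, and define normal numerically.
5. Include unscheduled and repeat values in the new rows, as SAP Section 7 does for the PCS analysis. SAP 6.1 ties any post-baseline value to scheduled visits where applicable, and SAP 3.9.2 limits laboratory summaries to scheduled values, so the rule for these rows has to be written out. Changing the baseline condition alone would not make the 3x ULN count match the PCS table; the set of visits must match too.

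The cost is a short SAP edit and a few extra table rows. It needs no new data and no change to eligibility or subject management.

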#### **7.2.6. General Exclusion Criteria**

24. Subject is currently pregnant or breastfeeding, or is planning to become pregnant during the study period.

25. Subject has any finding that, in the view of the investigator, would compromise the subject's ability to fulfill the protocol visit schedule or study requirements

26. Subject is currently under involuntary hospitalization or incarceration

27. Subject has participated in another clinical trial in which the subject received an experimental or investigational drug or agent within 6 months before screening by self-report or through confirmation using an clinical trial subject registry

28. Subject has participated in a clinical study with ALKS 3831 or samidorphan at any time

29. Subject is employed by Alkermes, PPD or study site (permanent, temporary contract worker, or designee responsible for the conduct of the study) or is immediate family\* of an Alkermes, PPD or study site employee

(\* Immediate family is defined as a spouse, parent, sibling or child, whether biological or legally adopted)

### 7.3. Subject Withdrawal

A subject may be discontinued from the study at any time if the subject, investigator, or sponsor determines that it is not in the best interest of the subject to continue participation. Reasons for discontinuation include:

- Adverse Event
- Lack of Efficacy
- Lost to Follow-up
- Withdrawal by Subject
- Protocol Deviation (non-compliance with study drug or study procedures)
- Pregnancy
- Study Terminated by Sponsor
- Other

Additionally, if a subject has an  $ANC < 1.0 \times 10^3 \mu L$  or  $HbA1c \geq 6.5\%$  at any time from Visit 2 to Visit 6, the PI (or designee) should discontinue the subject from participation immediately.

If a subject withdraws from the study for any reason, any ongoing AEs will be followed until resolution, until deemed stable by the investigator, or until the subject is deemed by the investigator to be lost to follow-up. If, in the opinion of the investigator, it is necessary to monitor a subject beyond the safety follow-up visit, the follow-up period may be extended as necessary. In such instances, the sponsor and the investigator will agree to an acceptable follow-up schedule.

In the event that a subject chooses to withdraw from the study, the investigator should make a reasonable effort to ascertain the reason(s) for withdrawal, while fully respecting the subject's rights. Randomized subjects are to be asked to return to the clinic for an early termination (ET) visit and to complete a subsequent safety follow-up period. The early termination visit should be scheduled as close as possible to the subject's last dose and will mimic the assessments scheduled to be conducted at Visit 6. If the subject fails or refuses to return to the study center, an attempt must be made to contact the subject by telephone in order to assess as many safety and efficacy parameters as possible. All data collected over the telephone must be documented and kept in the subject's record.

The investigator must maintain a record of all subjects who fail to complete the study. A full explanation of the reason for study discontinuation will be made on the appropriate electronic case report form (eCRF).

A subject will be deemed lost to follow-up after 3 attempts at contact have been made and it has been at least 1 month since the last subject contact. The 3rd attempt at contact must be a certified letter accompanied by a survey inquiring the reason for study discontinuation. All attempts at contact will be documented. The reason for discontinuation will be documented. If the PI becomes aware of a change in the subject's status or receives more information about a subject's disposition, this information will be documented.

#### **7.4. Replacement of Subjects**

Subjects prematurely discontinued from the study post randomization will not be replaced.

#### **7.5. Identification of Informant or Caregiver**

In some cases a caregiver may be required for a subject to join the study (eg, by a local institutional review board [IRB]). This person should be in contact with the subject, able to help with adherence to study procedures (including attending study visits when needed), and able to report on the subject's safety and behavior.

#### **7.6. Withdrawal and Replacement of Caregiver**

Some sites may require the caregiver to sign a caregiver ICF (separate from a subject ICF). A caregiver who is required to sign a caregiver ICF may withdraw consent at any time, in which case he/she can no longer fill the caregiver role for this study. Any other caregiver may decide to stop cooperating with study staff or be lost to follow-up, in which case he/she can no longer fill the caregiver role for this study. If a caregiver can no longer fill the caregiver role, he/ she should be replaced if possible. If the caregiver cannot be replaced, most subjects will be able to continue in the study. If the subject must also withdraw from the study (eg, the caregiver provided transportation to the site and no other travel arrangements can be made for the subject), the PI should make a reasonable effort to ascertain the reason(s) for the caregiver's withdrawal, while fully respecting the caregiver's and subject's rights. A full explanation about the caregiver's withdrawal should be included with explanation of the subject's discontinuation in the appropriate eCRF.

